2 VERSION HISTORY

Version number and Date	Reason for update
1.0	Initial version
2.0	Inclusion criteria #1 updated following EC review

3 CLINICAL PROTOCOL SUMMARY

Name of Company: Mundipharma (China) Pharmaceutical Co., Ltd.										
Name of Finished Product: Buprenorphine Transdermal Patch 20 mg and 40 mg	Name of Active Ingredient: Buprenorphine									
Protocol No.: BUP14-CN-101	<eudract><ind> No.: N/A</ind></eudract>									

Registration: https://register.clinicaltrials.gov

Short Title of the Study: A single dose PK study of Buprenorphine Transdermal Patch (20 mg, 40 mg application for 3 days and 40 mg application for 4 days) in Chinese subjects with chronic pain.

Full Title of the Study: An open-label, randomized, single-dose, parallel-group study to investigate the pharmacokinetic profile of single dose Buprenorphine transdermal patch 20 mg applied for 3 days, 40 mg applied for 3 days and 40 mg applied for 4 days in Chinese subjects with chronic pain.

Objectives:

Primary

To evaluate the pharmacokinetic (PK) profile of buprenorphine and its primary metabolite, norbuprenorphine of single dose buprenorphine transdermal patch (BUP TDS) 20 mg applied for 3 days, 40 mg for 3 days and 40 mg for 4 days.

Secondary

To evaluate the safety and tolerability following a single application of BUP TDS.

Sample size and Investigator(s)/Site(s):

[figure not shown]
Total sample size of 45 subjects (15 subjects/arm) will be randomised to receive IMP with the aim to have at least 36 subjects (12 subjects/arm) completing the study and providing valid PK data. The study will be conducted in 1-3 sites in China.

Summary of Study Design:

This is an open-label, randomised, single-dose, 3 arms study design. Subjects will be randomised into one of 3 arms, in a 1:1:1 ratio, wearing BUP TDS 20 mg for 3 days or 40 mg for 3 days or 40 mg for 4 days.

Study Diagram

20mg/3d = BUP TDS 20 mg application for 3 days 40mg/3d = BUP TDS 40 mg application for 3 days 40mg/4d = BUP TDS 40 mg application for 4 days

5 LIST OF ABBREVIATIONS

ADR Adverse Drug Reaction

AE Adverse Event

ALT Alanine transaminase (also SGPT)
AST Aspartate transaminase (also SGOT)

AUC Area under the plasma concentration-time curve

AUCt Area under the plasma concentration-time curve calculated from the time of

dosing to the last measurable concentration

BP Blood Pressure
bpm Beats per minute
BMI Body Mass Index
BUP Buprenorphine

CA Competent Authorities CS Clinical Significant

cm centimeter

Cmax Maximum observed concentration

CRF Case Report Form

CRO Contract Research Organisation

CYP Cytochrome

D Day

DMP Data Management Plan
DRM Data Review Meeting
EC Ethics Committee
ECG Electrocardiogram

eCRF Electronic Case Report form
EDC Electronic Data Capture

EDTA Ethylenediaminetetraacetic acid

EU European Union

EudraCT European Union Drug Regulating Authorities Clinical Trials

FDA Food and Drug Administration

GCP Good Clinical Practice

q gram

GGT Gamma-glutamyl-transferase
GLP Good Laboratory Practice

H Laboratory value above the reference range

h Hour hrs hours

HB_sAg Hepatitis B surface antigen HCV Ab Hepatitis C virus Antibodies hCG Human chorionic gonadotropin

HCO₃- Bicarbonate

HIVAb Human immunodeficiency virus antibodies

IB Investigator Brochure
ICF Informed Consent Form
I/E Inclusion/Exclusion

ICH International Conference on Harmonisation of Technical Requirements for

Registration of Pharmaceuticals for Human Use

IMP Investigational Medicinal Product

IRB Institutional Review Board

kg Kilogram

L Laboratory value below the reference range

LC-MS/MS Liquid Chromatography - Tandem Mass Spectrometry

LDH Lactate dehydrogenase

LLN Lower limit of the laboratory reference (normal) range

LNH Classification according to whether the Laboratory test result was below

(L), within (N), or above (H) the reference range

µg Micrograms m Meter

MAH Marketing Authorisation Holder

MCPC Mundipharma (China) Pharmaceutical Co., Ltd

MOA Monoamine oxidase

mg Milligram mL Millilitre

mmHg Millimetre mercury

N Laboratory value within the reference range

NCS Non Clinical Significant

NIMP Non-Investigational Medicinal Product/Auxillary Product

NMPA National Medical Products Administration

NRS Numeric Rating Scale
PIS Patient Information Sheet

PK Pharmacokinetic
PR Pulse rate
PT Preferred Term
QA Quality Assurance
RBC Red blood cell (count)
RSI Reference Safety Infor

RSI Reference Safety Information
SAE Serious Adverse Event
SAP Statistical Analysis Plan
SAS Statistical Analyses Software
SMP Safety Management Plan

SmPC Summary of Product Characteristics

SOC System Organ Class

SOPs Standard Operating Procedures t1/2Z Apparent terminal phase half-life

tmax Time from dosing to the maximum observed concentration

TEAA Treatment Emergent adverse event TDS Transdermal Delivery System

ULN Upper limit of the laboratory reference (normal) range

USA United States of America
WBC White blood cell (count)
WHO World Health Organisation

6 STUDY CONDUCT AND OVERSIGHT

6.1 Sponsor

This study will be conducted by qualified Investigators under the Sponsorship of Mundipharma (China) Pharmaceutical Co., Ltd (MCPC).

6.2 Declaration of Ethical Conduct

This study will be conducted in accordance with the standard operating practices of the Sponsor and Contract Research Organisation (CRO), which are designed to ensure adherence to Good Clinical Practice (GCP) guidelines as described in Section 16 of this protocol.

6.3 Investigators and Study Personnel

The study will be conducted in 1-3 centres in China. The contact details of the Investigator and other contact persons at the Sponsor and CRO will be listed in the study site file.

6.4 Data Management

All data management related tasks will be outsourced to a CRO. The Data Management Plan (DMP) will include a task and responsibility list for all data management tasks.

Clinical data will be captured by using an Electronic Data Capture (EDC) system. Quality control and data validation procedures will be applied to ensure the validity and accuracy of the clinical data. The Monitoring Plan and supporting documents will detail the data entry, source data verification, data validation, and locking procedures to be followed by all relevant study staff. The DMP describes the data flow between the EDC system, external vendors (e.g. lab) and different functional parties involved in the handling of clinical data.

At the end of the study each site will be provided with an archiving media including one PDF per subject with the clinical data and audit trail extracted from the EDC system.

6.5 Monitoring

The study will be monitored by qualified personnel from the CRO. The Monitoring Plan for the study will detail this process. The Investigator will allow monitoring, audit and inspection of the clinical, laboratory, and pharmacy facilities as required, to assure compliance with GCP and Good Laboratory Practice (GLP) as applicable. The EDC system and subject's corresponding original medical records (source documents) are to be fully available for review by the CRO/Sponsor's representatives at regular intervals. These reviews verify adherence to study protocol and data accuracy in accordance with local regulations and GCP. All records at the site are subject to inspection by the local competent and local health authorities.

6.6 Medical Monitoring & Safety

The name of the Study Physician along with the telephone and fax numbers of the other contact persons at the Sponsor and CRO are listed in the contact list stored in the study site file. 24-hour medical support will be provided by the CRO; the contact details are supplied in the Investigator Site File.

6.7 Central Review/Central Laboratory/Bioanalytical Laboratory

Local laboratories will be used for sample analysis for safety assessment. A qualified bioanalytical laboratory will be employed to process all study samples to generate bioanalytical data.

7 INTRODUCTION

7.1 Therapeutic Area/Background

Pain is one of the most common symptoms for cancer patients, seriously affecting their quality of life. The incidence of pain is about 25% in newly diagnosed cancer patients and around 60% to 80% in advanced cancer patients, where one third is assessed as severe pain (China Ministry of Health, Cancer pain clinical guidelines, 2011).

Pain is classified on the basis of its duration (i.e. acute and chronic pain) and underlying pathophysiology (i.e. nociceptive, neuropathic, mixed and psychogenic pain). Cancer pain patients commonly experience more than one kind of pain. The highest prevalence of pain (>85%) is related to cancers of pancreas, bone, brain, lung and head and neck.

Current treatment of cancer pain is based on the World Health Organisation's (WHO) concept of an "analgesic ladder" which involves a stepwise approach to the use of analgesic drugs and is essentially a framework of principles rather than a rigid protocol (WHO, 1996). This three-step approach is broadly established and 80 - 90% effective for the treatment of malignant and non-malignant pain.

Opioids are the mainstay of pain management for patients with moderate-to-severe cancer pain and are increasingly used for the treatment of chronic pain that is non-malignant in origin. Buprenorphine containing formulations are considered step III agents in the WHO analgesic ladder for pain.

7.2 Investigational Medicinal Product (IMP)

Buprenorphine is a synthetic opioid analgesic derived from the opium alkaloid thebaine. It is a μ -opioid receptor agonist, while it shows an antagonistic effect on κ -opioid receptors (Cowan *et al*, 1977). The analgesic potency of buprenorphine was found to be 25-50 times higher (on a weight-by-weight basis) than that of morphine (Budd, 2002).

With the indication for alleviation of moderate/severe pain, buprenorphine injection was first launched in the United Kingdom in 1978 and in the United States in 1982. It was mainly used for postoperative pain control, but also used for alleviation of moderate to severe pain in patients with cancer, trigeminal neuralgia, ureteral stones, myocardial infarction, and trauma. Moreover, a

sublingual tablet (Subutex®) was approved as a treatment for opioid dependency at doses of up to 16 mg/day, which was well above the analgesic range. Through international clinical experience for almost 4 decades, the safety and efficacy of buprenorphine for treating various types of moderate and severe pain have been demonstrated (Heel *et al*, 1979; Hoskin & Hanks, 1991; Lewis, 1995; Wolff *et al*, 2012). Pharmacokinetics of buprenorphine was found to be dose-proportional after both sublingual and intravenous administration (Walsh *et al.*, 1994; Budd, 2002). In China, buprenorphine injection and sublingual tablet were approved in 1995 and 1997 respectively, and used for many kinds of pain treatment.

However, the immediate-release formulations administered sublingually showed marked fluctuations of buprenorphine plasma concentration, i.e. high peak and low trough concentration during a dosing interval, which tend to induce inconsistent pain relief at trough or increased adverse events (AEs) at peaks. Oral formulations are not available for buprenorphine as the absolute bioavailability was found to be insufficient to achieve analgesic drug concentrations (Tegeder *et al.* 1999) due to the high first-pass effect.

In order to achieve a sustainable analgesic effect, the 3-day buprenorphine transdermal patch (Transtec®) was developed in the 1990s, and firstly approved in Switzerland in June 2000, for the management of moderate to severe cancer pain and severe pain refractory to non-opioid analgesics. As of August 2017, it has been approved in 32 countries worldwide but not yet in China.

The transdermal patch consists of a polymer matrix in which the active substance buprenorphine is dispersed. When applied to the skin, buprenorphine is continuously released from the matrix leading to constant transdermal invasion of the drug into the systemic circulation. The rate-controlled release of buprenorphine from the transdermal patch ensures relatively constant plasma levels which translate into long-term and consistent pain relief with the chance of minimizing the potential for of side effects.

Three dose strengths of Transtec® have been developed containing 20, 30, or 40 mg buprenorphine. The in-vivo release rates were found to be 35 μ g/h, 52.5 μ g/h, and 70 μ g/h over 72 hours (3 days), respectively. Plasma concentrations increased in a linear fashion according to dose.

After the initial application of Transtec®, the minimum clinically effective plasma concentration (100 pg/ml) was reached in about 11 hours for 70 μ g/h patch and about 21 hours for 35 μ g/h patch, and t_{max} across patch strengths was found to be 60 – 80 hours on average. After removing the patch, a steady decrease of plasma concentrations occurred about 1 hour later. The average terminal half-lives across patch strengths ranged from 20 to 27 hours.

Buprenorphine is metabolized in the liver, primarily to norbuprenorphine glucuronide (Kacinko *et al*, 2009). Cytochrome P450 (CYP) 3A4 is the phase 1 enzyme involved in metabolism of buprenorphine to norbuprenorphine (Kacinko *et al*, 2009).

Biliary excretion is the predominant route of elimination. After intravenous administration of buprenorphine, only 10% to 27% of the administered drug was excreted in urine. The faeces contain mainly unchanged buprenorphine, while urinary excretory products are conjugates of the parent compound and norbuprenorphine (Hand *et al*, 1986; Heel *et al*, 1979).

Clearance of buprenorphine was shown to be relatively independent of the renal system and is not altered in patients with renal impairment (Hand et al, 1990). Administration of the buprenorphine transdermal patch was found to be safe in these patients (Filitz et al, 2006). Neither buprenorphine nor norbuprenorphine plasma levels were found to be elevated. No

difference in pain relief before and after haemodialysis was observed. No dose adjustment is needed in these patients.

Additional data showed that each patch could provide sustained delivery of buprenorphine for up to 4 days (Likar, 2005), thus enabling the patient to change the patch twice a week, e.g. always on Monday and on Thursday. This is expected to improve the convenience of the usage of buprenorphine patch and positively contribute to the compliance of patients.

In addition to the 3 - 4 day patch, a 7-day patch formulation has been developed by Mundipharma / Purdue (Butrans® or Norspan®) and was first approved in Denmark in 2003. Since then, with the main indication of non-cancer pain, it has been approved in 47 countries up to January 2018. In the USA, 3 doses of buprenorphine (5, 10 and 20 mg with a release rate of 5, 10 and 20 μ g/h, respectively) were approved by the FDA in July 2010 for management of moderate to severe chronic pain requiring 24-hour sustained opioid analgesia. The 7-day buprenorphine patch was launched in China in December 31st, 2012 under trade name of Norspan®.

7.3 Study Rationale and Aim

The aim of this study is to evaluate the pharmacokinetic (PK) profile of buprenorphine and its primary metabolite, norbuprenorphine, after a single dose of buprenorphine transdermal patches being applied in Chinese subjects. The safety of buprenorphine transdermal patches will also be evaluated in the study.

This study consists of three treatment arms. Subjects will be randomised in a 1:1:1 ratio to BUP TDS 20 mg for 3 days, or BUP TDS 40 mg for 3 days or BUP TDS 40 mg for 4 days. The doses chosen cover the lowest and highest doses to be used in clinic in the future. These doses have been found to be well tolerated to date. The known and potential risks are those described in the latest version of the Investigator Brochure (IB).

Per Technical Guideline for Pharmacokinetic Studies of Chemical Drug Products (NMPA, 2005), if the drug will be used in clinics consecutively for multiple times, its PK characteristics at steady state with multiple administrations should be identified. This will be completed in a second PK study, BUP18-CN-101.

According to the regulations on narcotic drugs and psychotropic substances (State Council Order No. 442), the clinical trials of narcotic drugs and the first class psychotropic substances are not allowed to be conducted in healthy populations, the participants will therefore be chronic mild pain patients.

7.4 Design Rationale

The study design and data analysis follow the recommendations issued from the "Technical Guideline for Pharmacokinetic Studies of Chemical Drug Products prepared by China National Food and Drug Administration (NMPA, 2005) and from Pharmacopoeia of the P.R.C. (2015).

As the main study criterion is PK parameters which are objective and not subject to bias, an open label study design is therefore acceptable.

The plasma elimination half-life of buprenorphine is about 20-27 hours.

No formal sample size calculation was performed. The planned number of subjects will meet the requirement of the PK study guideline (NMPA, 2005), which recommends 8 to 12 subjects in each treatment arm.

The study will be conducted in compliance with the protocol, Good Clinical Practice (GCP), the ethical principles that have their origin in the declaration of Helsinki and the applicable regulatory requirements.

7.5 Benefit Risk Assessment

The safety and tolerability of buprenorphine are well established and generally regarded as favourable. Its safety profile has been described and summarized in a number of publications (Budd, 2002; Budd & Collett, 2003; Walsh *et al*, 1994; Dahan *et al*, 2005). Buprenorphine has been approved for more than 4 decades for intravenous and sublingual use in many countries, including the United States and many European countries.

The controlled-release method of buprenorphine administration via the transdermal matrix patch technology further enhances the safety margins of buprenorphine, without compromising the therapeutic value in the management of chronic pain in Chinese subjects.

Overall the assessment of all currently available published clinical data indicates a positive benefit-risk ratio of 3- or 4-day BUP TDS.

8 STUDY OBJECTIVES

8.1 Primary Objectives

 To evaluate the pharmacokinetic profile of buprenorphine and its primary metabolite, norbuprenorphine of single dose Buprenorphine transdermal patch (BUP TDS) 20 mg applied for 3 days, 40 mg for 3 days and 40 mg for 4 days.

8.2 Secondary Objectives

- To evaluate the safety and tolerability following single application of BUP TDS.

9 STUDY ENDPOINTS

9.1 Primary Endpoint

The primary endpoint will be the PK assessment. Pharmacokinetic parameters of the prototype buprenorphine, and the primary metabolite norbuprenorphine, calculated from plasma concentration-time data following a single application of BUP TDS 20 mg (3 days), 40 mg (3 days) and 40 mg (4 days).

9.2 Safety Endpoints

Subjects will be closely monitored throughout the study for evidence of any AE. Vital signs, including pulse rate, respiration rate, sitting blood pressure and body temperature, will be measured at regular intervals. Furthermore, examinations including physical examination, 12-

lead ECG as well as laboratory parameters, will be performed on the day of the last blood sample taken.

[figure not shown]

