- 18. Subjects who participated in a clinical research study involving a new chemical entity or an experimental drug within 30 days prior to the screening visit. Concurrent enrolment in another clinical trial is not permitted unless the sole purpose of the other trial is for collection of long-term follow-up/survival data.
- 19. Donated 400 mL or more of blood or blood products within 3 months prior to the start of the study.
- 20. Screening sitting blood pressure (BP) ≥140 mm Hg (systolic) or ≥90 mm Hg (diastolic), following at least 5 minutes of rest. If BP is ≥140 mm Hg (systolic) or ≥90 mm Hg (diastolic), the BP should be repeated two more times and the average of the three BP values should be used to determine the subject's eligibility.
- 21. 12-lead ECG demonstrating QTc>450 msec or a QRS interval >120 msec at Screening. If QTc exceeds 450 msec, or QRS interval exceeds 120 msec, the ECG should be repeated two more times and the average of the three QTc or QRS interval values should be used to determine the subject's eligibility.
- 22. Subjects who have history of hypersensitivity to opioid analgesic formulations.
- 23. Subjects who have history of hypersensitivity to naltrexone.
- 24. Subjects who have history of hypersensitivity to transdermal delivery system or patch adhesives.
- 25. Subjects with any potential dermatological disorder at a patch application site, e.g. previous and/or current unhealed extensive dermal damage in the area where the patch will be applied (e.g. dermatitis, burns, tattoos, scarring of the skin)
- 26. Subjects who could not discontinue therapy that involved direct heat sources (e.g. heat lamps, electric blankets, heating pads or heated water beds) for the duration of the study
- 27. Subjects with hairy areas who could not, or would not, cut the hair at the patch site for proper placement of the patch
- 28. Special diets such as caffeine or xanthine-containing foods and beverages (including pitaya fruit, mango, grapefruit, coffee, tea, cola, chocolate, grapefruit juice, etc.) should be taken within 48 hours before patch application or during the study.
- 29. Subjects who have difficulty swallowing tablets.
- 30. Subjects who cannot tolerate venipuncture, or subjects who have difficulty in collecting blood, or subjects who have a history of fainting at the sight of blood or needles.

31. Unwilling or suspected of not being able to comply with the study protocol.

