- Observe patch adhesion status once, just before patch removal.
- BUP TDS will be removed.
- BUP patch will be removed 72 hours (±2 minutes) after being applied.
- Prior to IMP removal PK sampling: PK blood sampling to occur in the last 2 minutes of dosing i.e. within 2 minutes before the patch is removed, a blood sample (6 mL) will be drawn.

- A blood sample (6 mL) will be drawn at 73, 74, 76 and 84 hours after administration of patch with a time window of ± 2 minutes for 73-76 hours and ±1 hour for 84 hours. Every effort should be made to ensure accurate sampling time and deviations should be kept to a minimum.
- Dermatological examination of patch application site will be conducted within 0.5 hour after patch removal using a 0 7 skin status scale refer to section 19.6.
- AE collection.
- Collection of concomitant medication and non-pharmacological therapies.

12.6.2.4 Day 05 and Day 07

- Vital signs (pulse rate, respiration rate, sitting blood pressure and body temperature) will be obtained in the morning within 30 minutes prior to PK blood sampling.
- A blood sample (6 mL) will be drawn at:
 - Day 05: 96 hours after patch application
 - Day 06: 120 hours after patch application.
 - Day 07: 144 hours after patch application.

Blood sample collection will be performed \pm 1 hour of scheduled time post dose. Every effort should be made to ensure accurate sampling time and deviations should be kept to a minimum.

- Dermatological examination of patch application site will be conducted in the morning of D05 and D06 using a 0 7 dermal response score (section 19.6). In case that the result of the examination conducted at D05 is judged "No evidence of irritation", the examination scheduled for D06 will not be conducted. In case AE was reported for the skin reaction and not recovered at D06, more examinations may be needed for the AE follow-up.
- AE collection.
- Collection of concomitant medication and non-pharmacological therapies.

12.6.2.5 Day 08

- A blood sample (6 mL) will be drawn at 168 hours after patch application. Blood sample
 collection will be performed ± 1 hour of scheduled time post dose. Every effort should be
 made to ensure accurate sampling time and deviations should be kept to a minimum.
- AE collection.
- Collection of concomitant medication and non-pharmacological therapies.
- The following procedures will only be conducted for 3-day application on Day 08 of the third period, or early termination:
 - Physical examination and weight

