- 50 mg of naltrexone tablet will be administered twice a day (every 12 hours) with 150 mL water in a standing position, with a time window of ±5 min based on scheduled time.
- Observe patch adhesion status once, just before patch removal.
- BUP patch will be removed 96 hours (±2 minutes) after being applied.
- Prior to IMP removal PK sampling: PK blood sampling to occur in the last 2 minutes of dosing i.e. within 2 minutes before the patch is removed, a blood sample (6 mL) will be drawn.
- A blood sample (6 mL) will be drawn at 97, 98, 100 and 108 hours after administration of patch, with a time window of ± 2 minutes for 97-100 hours and ±1 hour for 108 hours.
 Every effort should be made to ensure accurate sampling time and deviations should be kept to a minimum.
- Dermatological examination of patch application site will be conducted within 0.5 hour after patch removal using a 0 – 7 skin status scale – refer to section 19.6.
- AE collection.
- Collection of concomitant medication and non-pharmacological therapies.

12.6.3.4 Day 06 and Day 08

- Vital signs (pulse rate, respiration rate, sitting blood pressure and body temperature) will be obtained in the morning within 30 minutes prior to PK blood sampling.
- A blood sample (6 mL) will be drawn at:
 - Day 06: 120 and 132 hours after patch application
 - Day 07: 144 hours after patch application.
 - Day 08: 168 hours after patch application.

Blood sample collection will be performed ± 1 hour of scheduled time post dose. Every effort should be made to ensure accurate sampling time and deviations should be kept to a minimum.

- Dermatological examination of patch application site will be conducted in the morning of D06 and D07 using a 0 – 7 dermal response score (refer to section 19.6). In case that the result of the examination conducted at D06 is judged "No evidence of irritation", the examination scheduled for D07 will not be conducted. In case AE was reprized for the skin reaction and not recovered at D07, more examinations may be needed for the AE follow-up.
- AE collection.
- Collection of concomitant medication and non-pharmacological therapies.

12.6.3.5 Day 09

- A blood sample (6 mL) will be drawn at 192 hours after patch application. Blood sample
 collection will be performed ± 1 hour of scheduled time post dose. Every effort should be
 made to ensure accurate sampling time and deviations should be kept to a minimum.
- AE collection.

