15.7.5 ECG

The scheduled time-points for ECG assessment are presented in Section 12.

ECGs will be judged by the Investigator as clinically significant (yes/no). The number and percentage of subjects with clinically significant ECG findings will be summarised by dose group for each time-point.

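### The only scheduled post-dose ECG falls 96 h after patch removal and is tabulated only as clinically significant yes/no, so the ECG safety table holds no scheduled on-patch data

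*Combined protocol and SAP*

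**What the plan says.** The secondary objective in section 8.2 is "To evaluate the safety and tolerability following single application of BUP TDS". Section 9.2 names the ECG among the safety endpoints and fixes its post-dose timing: with the physical examination and laboratory tests, it "will be performed on the day of the last blood sample taken".

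- **ECG schedule.** Tables 1.1 and 1.2 mark ECGs at screening, Day 00, and Day 08 (3-day arms) or Day 09 (4-day arm). None is marked on a day when the patch is worn.
- **Removal and last sample, 3-day arms (section 12.6.2).** "BUP patch will be removed 72 hours (±2 minutes) after being applied"; on Day 08, "A blood sample (6 mL) will be drawn at 168 hours after patch application".
- **Removal and last sample, 4-day arm (section 12.6.3).** "BUP patch will be removed 96 hours (±2 minutes) after being applied"; the last sample is at 192 h on Day 09.
- **Analysis (section 15.7.5).** "ECGs will be judged by the Investigator as clinically significant (yes/no"; the number and percentage of subjects with such findings are then given by dose group and time-point. Sections 15.7.3 and 15.7.4 give laboratory values and vital signs descriptive statistics, change from baseline and shift tables.
- **Numeric ECG values.** These appear only in exclusion criterion 21 (section 11.2): "12-lead ECG demonstrating QTc>450 msec or a QRS interval >120 msec at Screening". For ECGs in general, section 12.1 asks for normal or abnormal, with abnormal results split by clinical significance.
- **Day label.** The Day 09 text in section 12.6.3.5 places the 4-day arm's final procedures, the ECG among them, on Day 08 of a third period. Table 1.2 marks them on Day 09, and this single-dose parallel study has no third period.

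**The concern.** An ECG is informative about the patch if it is recorded while drug is present, or if the effect persists after washout. Two of the three scheduled ECGs precede dosing and the third comes after most of the drug has gone. The binary summary then drops whatever numeric information the recordings hold, although the protocol treats QTc and QRS as meaningful enough to decide eligibility.

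At stake is the ECG part of the secondary objective. A table with no clinically significant findings would say little about the 20 mg and 40 mg patches during wear, and a reader of the report might not notice that no ECG was scheduled then.

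**Working it through.** The plan is descriptive (section 15.4) and gives no ECG margin, effect size or power, so there is no figure of its own to reproduce. The check is of timing first, then of the summary.

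**Inputs from the protocol.** Removal at 72 h and 96 h; last samples at 168 h and 192 h; half-life 20-27 h (section 7.4); average tmax 60-80 h (section 7.2); 15 randomised and at least 12 completing per arm (section 15.4).

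**1. Gap from removal to the post-dose ECG (nominal).**
- 3-day arms: 168 − 72 = 96 h.
- 4-day arm: 192 − 96 = 96 h.

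**2. Buprenorphine left, as a share of the removal-time level: 0.5^(gap / half-life).**
- Half-life 20 h: 96/20 = 4.8 half-lives, 0.5^4.8 = 3.6%.
- Half-life 27 h: 96/27 = 3.56 half-lives, 0.5^3.56 = 8.5%.
- 4-day arm if Day 08 were followed: gap 72 h, 0.5^(72/20) = 8.2% and 0.5^(72/27) = 15.7%.
- 3-day arms, counted from tmax: 168 − 80 = 88 h to 168 − 60 = 108 h. From a peak at 80 h, 0.5^(88/20) = 4.7% and 0.5^(88/27) = 10.4% of peak remain.

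No norbuprenorphine half-life is given, so these shares are for the parent drug only.

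**3. What that does to an effect that follows concentration.** Assume, for illustration, a 10 ms QTc effect at removal, proportional to concentration. At the late ECG it is 10 × 0.036 to 10 × 0.085, or about 0.4-0.9 ms. With n = 15, two-sided alpha 0.05, a normal approximation and an assumed SD of change of 8-15 ms, power for the within-arm change is 99.8% to 73% at removal and 5-7% at the late ECG, which is close to alpha. The 10 ms and the SD are not in the documents.

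**4. The yes/no summary.**
- With 0 of 15, the one-sided 95% upper bound is 1 − 0.05^(1/15) = 18%; with 0 of 12 it is 22%.
- A true rate of 5% gives no case in 15 subjects with probability 0.95^15 = 46%.

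These limits apply to any binary count of this size, whatever its timing.

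**5. Precision of a numeric summary.** The SD of QTc change is assumed at 8-20 ms.
- Within arm, n = 15: 2.145 × 8/√15 = 4.4 ms to 2.145 × 20/√15 = 11.1 ms (95% half-width).
- 20 mg versus 40 mg, 15 per arm: 2.048 × SD × √(2/15) = 6.0 ms to 15.0 ms.

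**The case against.** **The study has no ECG objective.** This is a descriptive pharmacokinetic study of a marketed patch, with no QT hypothesis or margin, and the late ECG belongs to an exit panel with laboratory tests and physical examination. That is correct, and it rules out calling this a power failure. But ECG is a named safety endpoint with its own by-time-point table, and no scheduled entry in that table comes from patch wear. Pulse and blood pressure are measured during wear but do not give QTc or QRS.

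**A reader might infer that no ECG can exist during exposure, or that no drug effect could be seen.** The documents do not support either. Subjects who stop early get the exit ECG (sections 12.6.2.5 and 12.6.3.5), unscheduled ECGs enter the eCRF (section 14.2), clinically significant findings become adverse events (section 12.1), and an effect that outlasts the drug could still show. None of these is a systematic on-patch measurement. Nor does the plan say that a clean table would be reported as cardiac safety.

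**An on-patch ECG is confounded.** Naltrexone runs every 12 h from the evening of Day 00 to the evening of removal (section 13.3), and section 12.6.1 lists the Day 00 ECG ahead of the first dose. Change from Day 00 therefore reflects patch plus naltrexone, and there is no naltrexone-only arm. Admission is by the afternoon and removal is in the morning, so time of day differs too. This stands for within-arm change. The 20 mg versus 40 mg 3-day contrast is randomised, with the same cover and clock times. It is imprecise, however: if the effect is proportional to dose, an assumed 10 ms at 40 mg gives a 5 ms contrast, against a half-width of 6-15 ms.

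**Interval values may not be on hand.** Criterion 21 requires QTc and QRS at screening only, and no correction formula is named. Section 15.1 would summarise continuous data in general, and details are deferred to the SAP, but section 15.7.5 specifies only the yes/no table. So a numeric summary is not free. Applied to the washout ECG alone it would add little.

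**Conclusion.** The point holds for scheduled ECGs and for effects that track exposure. In every arm the only scheduled post-dose ECG comes 96 h after removal, at about 3.6-8.5% of the removal-time buprenorphine level (8-16% in the 4-day arm if Day 08 were followed), and it is summarised only as yes/no. The shares rest on the protocol's half-life and first-order decline. The QTc precision, a half-width of about 4-11 ms per arm, rests on an assumed SD of 8-20 ms. This is a gap in assessing the secondary objective and is worth fixing. It is not an error in sample size and does not touch the primary endpoint.

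**What to change.** 1. **Timing.** Take the existing post-dose ECG on the day of removal while the patch is still on (Day 04 in the 3-day arms, Day 05 in the 4-day arm), before the adhesion check and the blood draw in the last 2 minutes. Keep the ECG at early termination. Subjects are already on site and the ECG count is unchanged. Cost: a schedule amendment, no routine discharge ECG, and care with the patch on the right upper chest. Keeping the discharge ECG as well would mean one extra recording per subject.
2. **Analysis.** Record QTc, with a named correction formula, and QRS at Day 00 and post-dose. In section 15.7.5 and the SAP, summarise values, change from Day 00 and counts of QTc above 450 ms by arm, beside the yes/no table. Say that within-arm change reflects patch plus naltrexone, and read the 20 mg versus 40 mg 3-day contrast, descriptively, for a dose effect. Cost: a few eCRF fields and one table.
3. **If the schedule is kept**, state in the report that no ECG was scheduled during patch wear.
4. **Day label.** Reconcile Day 08 of the third period in section 12.6.3.5 with Day 09 in Table 1.2.
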